## 7.6 **Technetium Scan and Radiation**

Subjects will undergo technetium scans of the salivary glands. In this procedure, they will receive an intravenous injection of 7 mCi of  $^{99m}$ technetium pertechnetate, which emits low-energy (approximately 140 kev) gamma rays. The effective radiation dose from the 2 scans will be 0.65 rem, which is below the maximum limit of 5 rem (0.05 rem) per year allowed for

research subjects by the NIH Radiation Safety Committee. Subjects will not be allowed to eat or drink anything except water and medications for 4 hours before the scan. If they have childbearing potential, they will be required to have a negative pregnancy test before the scan. The intravenous injection for the scan may cause discomfort or bruising at the needle site and, rarely, an infection may occur. Allergic reactions to technetium pertechnetate are also possible, but rare.

#### 7.7 Minor Salivary Gland Biopsy

Some subjects may require an MSG biopsy if one has not been completed within the past 5 years during Stage I Screening to confirm eligibility (Section 3.2). The biopsy will be performed according to NIDCR SOPs. Local anesthetic will be administered to minimize pain during the procedure. Biopsy of the MSG may cause discomfort, pain, and swelling at the site (usually lower lip) for several days following the procedure; these symptoms can be effectively treated with acetaminophen or more potent analgesics as needed. Subjects may also experience transient paresthesias in the region of the biopsy. Other possible risks are allergic reactions to the local anesthetic and bleeding and infection at the site of biopsy; however, such events are rare. The subject will be asked to sign a separate surgical consent form prior to the procedure.

## 7.8 Magnetic Resonance Imaging

During the study, subjects will undergo MRI scans of the parotid glands. These scans will be performed at the NIH Clinical Center Diagnostic Radiology Department under the direction of a radiologist. If not contraindicated, contrast agent will be used during the MRIs, which may be conducted with or without sedation. For each MRI scan, the subject will have to lie in the scanner for approximately 30 minutes, and will have to lie still for up to 10 minutes at a time.

Persons are at risk for injury from the MRI magnet if they have pacemakers or other implanted electrical devices, brain stimulators, some types of dental implants, aneurysm clips (metal clips on the wall of a large artery), metallic prostheses (including metal pins and rods, heart valves, and cochlear implants), permanent eyeliner, implanted delivery pump, or shrapnel fragments. Welders and metal workers are also at risk for injury because of possible small metal fragments in the eye, of which they may be unaware. Subjects will be screened for these conditions before having the scan, and those determined to have any will not be allowed to undergo MRI without

approval of the radiologist. Each subject will be asked to remove all magnetic objects (e.g., watches, coins, jewelry, and credit cards) before entering the MRI scan room.

It is not known whether MRI is completely safe for a developing fetus. All subjects of childbearing potential will have a urine or serum pregnancy test performed within 24 hours before each MRI scan. The MRI scan will not be performed if the pregnancy test is positive.

Subjects who fear confined spaces may become anxious during the MRI. If sedation is necessary, oral diazepam or another benzodiazepine recommended by the radiologist will be offered prior to the study (all screening and consents will be administered before the subject receives any sedation). Subjects with back problems may also experience back pain or discomfort from lying in the scanner. The noise from the scanner is loud enough to damage hearing, especially in persons who already have hearing loss. Subjects will be fitted with hearing protection during the scan. All subjects will be asked to complete an MRI screening form for each scan. There are no known long-term risks associated with MRI scans.

As part of the MRI scans, it is planned that subjects receive an IV injection of contrast agent containing gadolinium. The risks of an intravenous catheter include bleeding, infection, or inflammation of the skin and vein with pain and swelling. These events will be treated if they occur. Symptoms from the contrast infusion are usually mild and may include coldness in the arm during the injection, a metallic taste, headache, and nausea. Possible mild allergic reactions include rash, sweating, and itching. In an extremely small number of patients, more severe symptoms have been reported, including shortness of breath, wheezing, urticaria, and hypotension. Persons with renal failure are also at risk for a serious reaction to gadolinium contrast called nephrogenic systemic fibrosis, which has resulted in a very small number of deaths. Subjects will be asked about past allergic reactions to MRI contrast agents and impaired renal function prior to undergoing MRI. Serum renal function test results will also be available to the principal investigator and radiologist at the time of the MRI. The contrast agent will be omitted during the scan if hypersensitivity to gadolinium containing contrast agents is suspected, or if the subject is thought to be at increased risk for nephrogenic systemic fibrosis (glomerular filtration rate <60 mL/min).

#### 7.9 **Blood Collection**

Blood will be drawn from subjects. Approximately 16.5 mL of blood will be drawn during Stage I and Stage II screening; approximately 30 mL on Days 0 and 28; and approximately 24 mL on Day 56. The total volume of blood drawn during the entire study will be approximately 154.5 mL. If clinically indicated, some subjects may have blood drawn at the Safety Follow-up.

Subjects may experience discomfort, bleeding, or bruising at the venipuncture site, which should resolve with time. There is also a small risk of fainting. Pressure will be applied to the venipuncture site for several minutes after needle removal to prevent bruising or bleeding. Infection at the site of needle insertion may also occur but is rare with the use of sterile disposable needles and aseptic technique. The amount of blood drawn for research purposes will be kept within the NIH guidelines for adults, not exceeding 10.5 mL/kg or 550 mL, whichever is smaller, over any 8-week period.

#### 7.10 Risk of stopping salivary stimulants

Subjects will be required to suspend the use of salivary stimulants within 24 hours prior to each study visit, and this suspension could cause discomfort from dryness of the mouth.

### 7.11 Unexpected Adverse Events

Unforeseen adverse effects are a risk with every new drug treatment, including new routes of administration for approved drugs. The risks of participating in this study are reasonable relative to the potential health benefits and generalizable medical knowledge that may be obtained.

### 8 SUBJECT SAFETY MONITORING

All subjects will be monitored from the time of informed consent. Study procedures will be performed and monitored by licensed/certified NIH personnel. At each study visit, subjects will be evaluated for AEs and will be followed until resolution or stabilization of any AEs. All AEs will be graded according to a descriptive severity scale based on the National Institute of Allergy and Infectious Diseases (NIAID), Division of Acquired Immunodeficiency Syndrome Table for Grading the Severity of Adverse Events. The scale has been slightly modified for this protocol (Appendix 24.4 ). Pregnancy will be monitored throughout the study and subjects study participation will be stopped in the event of pregnancy. Emergency unblinding of a subject's

parotid gland randomization assignment will be allowed if the information is needed to treat a serious adverse event.

Serious adverse events will be reported to CROMS Product Safety group; each event will be reviewed by a CROMS medical monitor. The site's medically responsible Investigator will determine follow-up actions based on event intensity and whether it was expected and at least possibly related to study drug.

Subjects will be informed that they may withdraw or be excluded from the study at any time. The following conditions will require the discontinuation of study drug:

- Pregnancy
- New onset of a condition that requires treatment with any prohibited agent (Sections 3.3 and 6.2).
- Inability of study personnel to cannulate one or both parotid glands.
- Noncompliance with study procedures.
- Adverse event that would substantially increase the risk of continued participation.
- Investigator discretion.
- Violation of eligibility criteria.

Subjects who stop study treatment after receiving 1 of the two doses will be asked to complete the Day 56 assessments and the Safety Follow-up, excluding core needle biopsy of the parotid. Subjects who qualify for the study and who, prior to the first dose of study medication, elect to not receive treatment, will have the following assessments:

- Evaluation of AEs.
- Vital sign measurements (pulse rate, systolic and diastolic blood pressure, respiratory rate, and temperature).
- Laboratory tests if clinically indicated.

No additional data will be collected from subjects who withdraw completely from the study.

### 9 OUTCOME MEASURES

#### 9.1 **Primary Outcome Measure**

The primary endpoint of the study is the change in salivary flow from Day 0 to Day 56.

#### 9.2 Secondary Outcome Measures

Secondary endpoints include the following:

- Change in focus score on parotid biopsy from Stage II screening to Day 56.
- Changes in salivary flow from Day 0 to study Days 14, 28, 42, and 56.
- Changes in assessments on the Patient Dry Mouth Questionnaire from Day 0 to study Days 14, 28, 42, and 56.
- Changes in assessments on the Sjögren's Disease Activity Index from Day 0 to study Days 14, 28, 42, and 56.
- Changes in other assessments of salivary function from baseline to study Day 56, including technetium scan of the salivary glands.
- Changes in laboratory measures of inflammation.
- Frequency of AEs related to treatment; location of the AE (body site, right or left), will be recorded and evaluated, as applicable.

Exploratory endpoints will be the changes in mechanistic endpoints from baseline to study Days 14, 28, 42, and 56.

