## Secondary Endpoints

- Change in focus score on parotid biopsy from Stage II Screening to Day 56.
- Change in salivary flow from Day 0 to study Days 14, 28, 42, and 56.
- Changes in assessments on the Patient Dry Mouth Questionnaire from Day 0 to study Days 14, 28, 42, and 56.
- Changes in assessments on the Sjögren's Disease Activity Index from Day 0 to study Days 14, 28, 42, and 56.

- Changes in other assessments of salivary function from baseline to study Day 56, including technetium scan of the salivary glands.
- Changes in laboratory measures of inflammation.
- Frequency of AEs related to treatment; AE location (body site, right or left), will be recorded and evaluated, as applicable.

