#### 2.2 Secondary Objectives

Secondary objectives of the study include the following:

• To perform mechanistic studies to determine the mechanisms of action of low-dose topical corticosteroid irrigation of the parotid gland.

- To assess biomarkers of inflammation and salivary gland dysfunction in SS subjects treated with low-dose topical corticosteroid irrigation of the parotid glands.
- To assess localized safety of dexamethasone irrigation of the parotid gland, as compared with placebo.

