# 7.3 Parotid Fill Volume Determination and Saline Irrigation of Parotid Gland

Parotid fill volume will be measured before irrigations. Each subject will undergo 3 irrigations of each parotid gland, the first of which will use saline only. This procedure will involve placement of a catheter within Stensen's duct and filling of the duct with the appropriate solution, either dexamethasone or normal saline. The procedure may cause minor trauma to the parotid ducts and/or infection or inflammation of the parotid gland (sialadenitis). Other rare risks include perforation and/or scarring of the parotid duct(s) and damage to the facial nerve secondary to inflammation, infection, or scarring.

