## 7.4 Intraductal Dexamethasone

Dexamethasone sodium phosphate is a synthetic adrenocorticosteroid indicated for a variety of disorders associated with inflammation. Like other glucocorticoids, it can cause profound and varied metabolic effects, as well as modify the body's immune responses to diverse stimuli. At equipotent anti-inflammatory doses, dexamethasone almost completely lacks the sodium-retaining property of hydrocortisone and closely related derivatives of hydrocortisone. Dexamethasone is contraindicated in persons with systemic fungal infections and in persons with hypersensitivity to any component of the formulation.

In this study, dexamethasone will be used topically in small doses within the parotid ducts; therefore, systemic exposure to the drug is expected to be extremely low. The dose (2 mg given twice 4 weeks apart) is within the range approved for intra-articular/intralesional use (0.2 to 6 mg administered once every 3 to 5 days to once every 2 to 3 weeks). Possible risks from local exposure in the mouth include irritation of the oral mucosa, temporary unpleasant taste, and increased risk of infection, allergic reaction, and pain. The risks associated with prolonged systemic exposure to dexamethasone (hypertension, diabetes, osteoporosis, glaucoma, increased risk of systemic infection, and adrenal insufficiency) are very unlikely to occur with this dosing regimen.

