# 17 ADVERSE EVENT, PROTOCOL DEVIATIONS AND UNANTICIPATED PROBLEM REPORTING

The Principal Investigator is responsible for detecting, documenting, and reporting unanticipated problems, adverse events (AEs), including serious adverse events (SAEs), and deviations in accordance with NIH policy, IRB requirements, and federal regulations. Relatedness to the research of all serious adverse events will be determined by the PI in consultation with the CD.

Serious unanticipated problems and serious protocol deviations will be reported to the IRB and CD as soon as possible and in writing on the Problem Report Form not more than 7 days after the PI first learns of the event. Not serious unanticipated problems and not serious deviations will be reported to the IRB and CD as soon as possible and in writing on the Problem Report Form not more than 14 days after the PI first learns of the event.

Deaths will be reported to the Clinical Director within 7 days after the PI first learns of the event.

All adverse events, deviations, and unanticipated problems will be summarized and reported at the time of Continuing Review.

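### The safety endpoint counts only AEs judged related to treatment, which is narrower than the randomised gland-versus-gland comparison of local safety that the objective calls for

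*Protocol*

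**What the plan says.** The safety objective in section 2.2, repeated in the précis, is "To assess localized safety of dexamethasone irrigation of the parotid gland, as compared with placebo". It carries no causality condition.

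The endpoint that serves it does. Section 9.2 gives "Frequency of AEs related to treatment; location of the AE (body site, right or left), will be recorded and evaluated", and the précis gives "Frequency of AEs related to treatment; AE location (body site, right or left), will be recorded and evaluated, as applicable".

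Collection is wider than the endpoint. Section 8 states: "At each study visit, subjects will be evaluated for AEs and will be followed until resolution or stabilization of any AEs". All AEs are also graded, and section 17 has them summarised for continuing review, without a comparison by gland. Section 10.1.1 defines a Safety Population, but section 10 describes no AE analysis.

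On causality, section 17 says: "Relatedness to the research of all serious adverse events will be determined by the PI in consultation with the CD". No role is named for judging non-serious events.

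**The concern.** Section 4.4.12 randomises dexamethasone to the left or right gland, with saline in the other. A local event has a side, and the side has a randomised treatment. The difference in local event frequency between glands is therefore protected by randomisation and needs no judgement about individual cases.

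The endpoint puts such a judgement in front of that comparison, in a setting where causes overlap:

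- Section 7.3 lists "infection or inflammation of the parotid gland (sialadenitis" as a possible result of the irrigation procedure.
- Section 7.4 lists "increased risk of infection, allergic reaction, and pain" for local dexamethasone exposure.
- Section 1 describes major gland enlargement as very frequent in the disease.
- Sections 4.4.9 and 7.5 have the right gland alone biopsied.

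A swelling or infection in a dexamethasone gland that is put down to disease or biopsy is not counted, even if such events are more frequent on that side. At stake is how well a small pilot can describe comparative local safety, which is one of its three secondary objectives.

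**Working it through.** **Textual check**

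1. *Objective against endpoint.* The objective is all local safety, dexamethasone versus placebo (2.2). The endpoint is the related subset (9.2 and précis). No other section defines an endpoint or gland comparison on all AEs. The restriction is stated twice, so an analysis plan that follows the protocol would inherit it.
2. *Related to what?* Section 9.2 refers to treatment. Section 15.3 uses study drug for some triggers, and study procedure or study drug for parotid infection. Section 17 refers to the research. The reference point of the endpoint is not settled.
3. *Can biopsy events be separated without a causality opinion?* Largely, yes. Footnote 6 of Table 4-1 puts the baseline biopsy at least 14 days before Day 0, and the second one after the Day 56 scans. Counting only onsets after the Day 0 irrigation sets aside baseline-biopsy events that began earlier. Right-gland events after the second biopsy can be identified by date and site.

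**Illustration of size**

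The protocol states no AE rate and no safety sample size, so there is no figure to reproduce. The 16 gland pairs come from section 10.2. The event rates and the share *q* judged related are assumptions. Glands are taken as independent, and *q* is the same for both glands, as blinding would imply.

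The expected gland difference becomes *q*(p_dex − p_sal). As a yardstick only, because the protocol plans no AE test, take an exact one-sided sign test at 0.05:

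- Per pair, P(event in dexamethasone gland only) = a = q·p_dex(1 − q·p_sal), and P(saline gland only) = b = q·p_sal(1 − q·p_dex).
- Discordant pairs K ~ Bin(16, a + b); of these, dexamethasone-only X ~ Bin(K, a/(a + b)).
- Reject if P(Bin(K, 0.5) ≥ X) ≤ 0.05.

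| p_dex, p_sal | q | a, b | Difference | Power |
|---|---|---|---|---|
| 40%, 10% | 1.0 | 0.360, 0.060 | 30 points | 43% |
| 40%, 10% | 0.7 | 0.2604, 0.0504 | 21 points | 23% |
| 40%, 10% | 0.5 | 0.190, 0.040 | 15 points | 11% |
| 50%, 10% | 1.0 | 0.450, 0.050 | 40 points | 67% |
| 50%, 10% | 0.7 | 0.3255, 0.0455 | 28 points | 41% |
| 50%, 10% | 0.5 | 0.2375, 0.0375 | 20 points | 21% |

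The chance of recording at least one event in 16 dexamethasone glands is 1 − (1 − q·p)^16. For p = 10% it is 1 − 0.90^16 = 82% with all events, 1 − 0.93^16 = 69% at q = 0.7, and 1 − 0.95^16 = 56% at q = 0.5.

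The model has one built-in limit. It removes events in the same proportion whatever their cause, so the filter can only lose signal. If the filter removed only background events that are equally frequent in both glands, the difference would stand and the noise would fall. The table shows what the filter can cost, not what it will cost.

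**The case against.** **Treatment may include the irrigation itself.** The protocol uses the word for irrigation of either gland: the title of 4.4.12, Table 4-1, the placebo treatment in 10.1.5 and the two irrigation treatments in 10.2. On that usage, an infection from cannulating either gland counts. A reader might infer from sections 7.3 and 7.4 that cannulation events are necessarily lost. The documents do not establish that. It follows only if treatment means the drug alone, and 9.2 does not say. This part of the objection stands. Events ascribed to disease or biopsy still drop out on either reading.

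**Blinding limits the harm.** A reader might also infer that the filter could favour dexamethasone, since no causality assessor is named and 4.4.12 has the words dexamethasone or saline on the vial labels. But the design is double-blind, section 8 allows unblinding only in an emergency, and 4.4.15 has investigators unblinded only after data analysis. With attribution blind to side, the filter acts alike on both glands and mainly dilutes. This also stands.

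**The data are kept, and tables belong to the analysis plan.** All AEs are collected, with side as applicable, so nothing is lost from the database. An analysis plan, which is not at hand, could add a table of all local AEs by gland. That limits the consequence but does not change the endpoint that the protocol fixes.

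**Every rate is assumed.** This is true. Section 1.1 even reports no adverse reactions to catheter irrigation in the earlier study of parotid corticosteroid irrigation.

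**Biopsy is always right-sided, and balance holds only on average.** This is also true. If sides were assigned by simple randomisation (an assumption), an 11:5 split or worse among 16 subjects has probability 2 × (1 + 16 + 120 + 560 + 1820 + 4368)/65536 = 21%. This argues for flagging biopsy-timed events. It does not argue for restricting the whole endpoint.

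**Other safeguards exist.** The section 15.3 triggers and the monitoring committee protect subjects, but they do not compare glands.

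**Conclusion.** The point holds in a limited form. The endpoint in 9.2 and the précis is narrower than the objective in 2.2. It replaces a comparison that randomised side already supports with one that first passes through individual attribution. Local events ascribed to disease or biopsy are excluded. Those ascribed to cannulation are excluded only on the narrower reading of treatment.

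The expected effect is dilution, given the blinding that the protocol describes. Its size cannot be derived from the protocol. Under the assumed rates and a common share of 50% to 70% judged related, the gland difference shrinks in the same proportion and power on the yardstick test falls to between roughly a quarter and three fifths of its value. The protocol does not support any particular loss of power, a bias in favour of dexamethasone, or a loss of AE data. The weakness is in the endpoint definition and is worth correcting because the correction is nearly free.

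**What to change.** In section 9.2 and the précis:

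1. Define the safety endpoint as the frequency of all AEs localised to one parotid or one side, with onset after the Day 0 irrigation. Tabulate them by the treatment that gland received, regardless of attribution.
2. Show AEs judged related as an added column, and state whether related covers the irrigation procedure as well as the drug.
3. Flag right-gland events with onset after the Day 56 biopsy, using date and site rather than a further causality judgement.

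Non-localised AEs cannot be assigned to a gland and can stay as a per-subject listing.

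The cost is a wording change and one extra table; no new data are needed. The downside is some noise from unrelated local events, which randomisation balances between treatments only in expectation. Showing all local AEs beside the related ones lets the reader see both.
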